#### ***2.1.4.2 Laboratory safety variables***

The clinical laboratory data to be analyzed include measures of hematology, clinical chemistry, renal function, liver function, and lipids. Clinical laboratory values will be analyzed in conventional units.

#### ***2.1.4.3 Vital signs variables***

Vital signs include weight, heart rate, and systolic and diastolic blood pressure in sitting position.

#### **2.1.5 Quality-of-life endpoints (KCCQ-12)**

A 12-item version of KCCQ-12 questionnaire was used in SOLOIST, capturing symptom frequency (4 items), physical (4 items) and social limitations (3 items), and quality of life impairment (2 items) as a result of having congestive HF (Appendix B Kansas City Cardiomyopathy Questionnaire). An overall summary score as well as 4 domain scores can be calculated ranging from 0 to 100 where 100 denotes the highest health status.

The KCCQ-12 was to be completed by all patients as described in the study flow chart of protocol. In case of premature permanent IMP discontinuation, the KCCQ-12 was to be completed by patients at the visit planned for the last dosing day with IMP and afterwards as normally planned.

## **2.2 DISPOSITION OF PATIENTS**

Screened patients are defined as any patients who signed the informed consent.

Randomized patients consist of all patients with a signed informed consent form who have had a treatment kit number allocated and recorded in the IRT database, regardless of whether the treatment kit was used. These patients form the randomized population.

For any patient randomized more than once, only the data associated with the first randomization will be used in any analysis population. The safety experience associated with any later randomization will be assessed separately. Patients who are not randomized will not be in the safety population.

For patient study status, the total number of patients in each of the following categories will be presented in the clinical study report using a flowchart diagram or summary table:

- Screened patients
- Screen failure patients and reasons for screen failure
- Nonrandomized but treated patients
- Randomized patients

- Randomized but not treated patients
- Randomized and treated patients
- Patients who complete the study treatment period as per protocol (as per e-CRF treatment status form)

Note: patients who die while on treatment will be treated as treatment completers

- Patients who discontinued study treatment by main reason for permanent treatment discontinuation (as per e-CRF treatment status form)
- Patients who complete the study as scheduled (i.e. subject status is death or completed on the Completion of end of study eCRF form or a study close-out visit was performed through alternative contact during the study close-out period)
- Patients who did not complete the study as scheduled and the reasons for study discontinuation
- Status at last study contact (as per e-CRF Subjects Status form)
- Patients who had known vital status during the study close-out period

Patients randomized but not treated will be included in the efficacy analysis.

The number (%) of patients who prematurely discontinued the study for primary efficacy events will be summarized. The main reason for study discontinuation will be summarized overall and according to whether or not the patients had a primary efficacy endpoint prior to study discontinuation. A patient will be considered as having discontinued the study for CV death, HHF, or urgent HF visit if the date of the last information on this endpoint (presence or absence) is before his/her scheduled Study Closeout Visit.

Duration of patient in study (Study duration regardless of on treatment or not) is defined as date of death or last known alive – randomization date + 1 day. The study duration will be summarized according to median, 25th percentile, 75th percentile, and range for each treatment group and for the overall population.

Additionally, the following populations will be summarized by treatment group:

- Randomized population
- Efficacy population: intent-to-treat (ITT) population
- Safety population

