|  | 
Analysis of other endpoints:
 
The analysis of other time to event endpoints will be performed using the same stratified Cox proportional hazards model as for the second primary endpoint, with LVEF (<50%, ≥50%) and region (North America, Latin America, Western Europe, Eastern Europe, and rest of the world) as stratification factors and treatment (sotagliflozin, placebo) as fixed effect factor. The LVEF factor will not be included in the statistical model as stratification factor if the endpoint is defined in subgroup of patients defined by LVEF (eg, LVEF<40%). Analysis of other endpoints will be descriptive with no statistical testing. Summary statistics at scheduled visits using observed data will be provided by each treatment group. Graphical presentations will also be used to illustrate trends over time if applicable.
 
Analyses of Safety Data:
 
All safety summaries will be descriptive; no statistical hypothesis tests will be performed on safety data. These analyses will be based on the safety population, which is defined as all randomized patients who receive ≥1 dose of double-blind treatment, regardless of the amount of treatment administered.
 |
| 
DURATION OF STUDY PERIOD (per patient)
 | 
The estimated study duration for a given patient will be approximately 3 to 32 months, assuming approximately 29 months of recruitment, and approximately 3 months of follow-up after the last patient is randomized.
 
All randomized patients (irrespective of whether they experienced efficacy event[s] or whether they permanently early discontinued double-blind treatment) will be followed from Randomization until their Follow-up Visit (or Study Closeout Visit, for patients who prematurely permanently discontinued from IMP) or death, whichever comes first.
   |
| 
STUDY COMMITTEES
                       | 
Executive Committee:  Yes  No
 
Steering Committee:  Yes  No
 
Data Monitoring Committee:  Yes  No
 
Adjudication Committee:  Yes  No
   |

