#### ***a. General censoring rule for primary efficacy endpoint:***

For patients who have no primary CV endpoints, they will be censored using the following rules:

- Patients who completed the study will be censored at their last study visit date (study close-out visit date or final follow-up visit date, whichever later).  
Note: If there are CV events happening after the patient's last study visit and the event's proceeding/related event's onset date is on or before the patient's last study visit date, in this case, this CV events will be included in efficacy analysis.

Another example, for a HHF, if the onset date of HF is before last study visit and its resulted hospitalization is after last study visit, this HHF will be included in efficacy analysis.

- Patients who died without discontinuing the study before death (ie Death reported on the 'Completion of End of Study') will be censored at their date of Non-CV death
- Patients who discontinued the study will be censored at their later of study discontinuation date or latest date with cardiovascular efficacy endpoint information (MI/UA, heart failure, cerebrovascular event, or coronary procedure, admission to hospital/emergency room, cardiac biomarkers) collected

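### The SAP 2.2 rule for premature discontinuation on the primary endpoint has no exception for death, which contradicts the completer definition in the same section

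*SAP*

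**What the plan says.** SAP Section 2.2 (Disposition of patients) announces a table: "The number (%) of patients who prematurely discontinued the study for primary efficacy events will be summarized". It then defines who is counted. With respect to the components of the primary endpoint, a patient is taken to have discontinued "if the date of the last information on this endpoint (presence or absence) is before his/her scheduled Study Closeout Visit". The main reason for discontinuation is to be shown overall and according to whether a primary event came before it.

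The disposition list earlier in the same section treats death differently:

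- One row is "Patients who complete the study as scheduled (i.e. subject status is death or completed on the Completion of end of study eCRF form"; a closeout visit made by alternative contact also qualifies.
- A note to the treatment-completion row adds that "patients who die while on treatment will be treated as treatment completers".

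Elsewhere, death is an ordinary end of observation:

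- Also in SAP 2.2, time in study "is defined as date of death or last known alive – randomization date + 1 day".
- SAP Appendix A, in the general censoring rule for the primary endpoint, has one line for "Patients who died without discontinuing the study before death" and a separate line for patients who discontinued.
- The protocol's Clinical Trial Summary follows all randomized patients to the Follow-up Visit, or to the Study Closeout Visit for those "prematurely permanently discontinued from IMP) or death, whichever comes first".

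**The concern.** The rule compares the date of last endpoint information with the scheduled closeout and does nothing else. For a patient who dies, the last possible information is at death. If death precedes closeout, the condition is met whether the death is cardiovascular or not, and however completely the patient was followed. That patient would be a completer in one row of the disposition table and a premature discontinuation in another.

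The count is meant to tell a reader how much primary-endpoint follow-up is missing. Within SAP 2.2 it is the only item defined by the date of last endpoint information; the others concern treatment, study status or vital status. That is useful in a trial closed early, because efficacy follow-up runs to the date last known alive (SAP 2.4.4), which can be later than the last endpoint information. A count that mixes deaths with withdrawals does not answer the question. If mortality differs between arms, it would also show a difference in apparent discontinuation that has nothing to do with missing data.

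**Working it through.** **Step 1. Apply both definitions in SAP 2.2 to five kinds of patient.** The documents state no figure to reproduce, so the check is one of classification.

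| Patient | Completer row | Discontinuation rule, read literally |
|---|---|---|
| Alive, closeout done | completed | not discontinued |
| Alive, withdrew early | not completed | discontinued |
| HHF, then followed to closeout | completed | not discontinued |
| CV death on study before closeout | completed | **discontinued** |
| Non-CV death on study before closeout | completed | **discontinued** |

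Only the two kinds of death conflict. A nonfatal primary event followed to closeout is classified correctly.

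**Step 2. Look at the split by prior primary event.** For a CV death with no earlier HHF or urgent visit, the event and the supposed discontinuation fall on the same date. Whether the event counts as prior is then unclear. Reasons are listed for patients who did not complete as scheduled, and that row excludes deaths.

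**Step 3. Look for a reference date for patients who died.** For days alive and out of hospital, SAP 2.4.4.4 assigns patients who died a reference date of May 1, 2020. SAP 2.2 assigns none for the discontinuation rule.

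**Step 4. Illustrate the size.** The documents give no mortality figure, so what follows is an assumption with a range.

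- True dropout: the 2% annual censoring rate in Protocol 11.1, applied for one year, gives 0.02 × 1000 = 20 per 1000.
- Assumed proportion dying on study before closeout: d = 5%, 10%, 15%, 20%.
- Reported count per 1000 = 20 + 1000 × d. The sum assumes that no patient is in both groups.

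| d | Reported per 1000 | Ratio to 20 |
|---|---|---|
| 5% | 20 + 50 = 70 | 3.5 |
| 10% | 20 + 100 = 120 | 6 |
| 15% | 20 + 150 = 170 | 8.5 |
| 20% | 20 + 200 = 220 | 11 |

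**Step 5. Illustrate the difference between arms.** Assume equal true dropout in both arms and a mortality hazard ratio of 0.81. That value is borrowed: Protocol 11.1 plans it for first CV death or HHF, not for mortality. With p the proportion dying on placebo, the proportion on sotagliflozin is 1 − (1 − p)^0.81.

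| Placebo p | Sotagliflozin | Apparent gap (points) |
|---|---|---|
| 5% | 4.1% | 0.9 |
| 10% | 8.2% | 1.8 |
| 15% | 12.3% | 2.7 |
| 20% | 16.5% | 3.5 |

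With no mortality difference the gap is zero.

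**Step 6. Apply the correction.** With patients who die on study exempted, the two definitions agree for all five kinds of patient. The count in Step 4 returns to 20 per 1000 at every d.

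**The case against.** The strongest reply is that the literal reading is not the only one. The rule refers to the patient's own scheduled closeout. Closeout timing is communicated only once the event date is projected (Protocol 10.1.4), and protocol follow-up ends at death. A patient who has died arguably has no scheduled closeout. The rest of the SAP keeps death apart from discontinuation, so a programmer would have good grounds for leaving deaths out. This stands in part: it cannot be said as fact that every death will be misclassified. But on this reading the rule says nothing about deaths, so a sentence is still needed. The reading is also strained, because Protocol 6.2.2 sets closeout for all randomized patients at the study level.

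Second, other rows in SAP 2.2 also describe completeness: completers with deaths included, non-completers with reasons, status at last contact, and vital status at closeout. This stands. The count is not the plan's sole evidence on missing follow-up, and a careful reader could partly reconstruct the correct picture.

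Third, the sizes rest wholly on assumed mortality. This stands too. Steps 4 and 5 show only how the rule behaves, and patients who drop out and later die would make the simple sum too large.

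**Conclusion.** The inconsistency is real and worth correcting, but its reach is small. Read literally, SAP 2.2 counts patients who die on study before closeout as premature discontinuations and also as completers. On the softer reading the rule is undefined for them. What is affected is one descriptive count of incomplete primary-endpoint follow-up and its split by prior primary event. That count would overstate missing follow-up, and could differ between arms if mortality does. The actual size is unknown; the 70 to 220 per 1000 and the 0.9 to 3.5 points depend on assumed death rates, an assumed dropout of 20 per 1000 for the counts, and a borrowed hazard ratio for the gap.

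A reader might infer that the rule biases the primary comparison, or that deaths are censored as dropouts in the efficacy analysis. The documents do not support that. The efficacy population is all randomized patients (SAP 2.3.2). Events count from randomization to the date last known alive (SAP 2.4.4). In the primary model CV death is an event and non-CV death a competing event (SAP 2.4.4.1). Appendix A sets its censoring dates without using the disposition rule.

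**What to change.** Replace the defining sentence in SAP 2.2 with wording to this effect:

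> A patient is considered to have incomplete follow-up for the primary endpoint if the patient did not die on study and the date of last endpoint information is before the Study Closeout Visit. Patients who die on study without having previously discontinued the study are complete through the date of death and are shown in a separate row. Patients who discontinued the study before death, with endpoint status not ascertained through the date of death, are incomplete.

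This uses the distinction that Appendix A already draws between dying on study and dying after discontinuation. It needs no notional closeout date for patients who died. For deaths, completeness should not be tested by asking whether the last information before death is earlier than the death date: that is always true and would bring the problem back.

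The cost is a short wording change in the SAP and a small change to one table program. No new data are needed and no inferential analysis changes.

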## **2.3 ANALYSIS POPULATIONS**

Patients treated without being randomized will not be considered randomized and will not be included in any efficacy population.

### **2.3.1 Randomized population**

The randomized population includes any patient who has been allocated to a randomized treatment regardless of whether the treatment kit was used.

For any patient randomized more than once, only the data associated with the first randomization will be used in any analysis population.

### **2.3.2 Efficacy population**

The efficacy analysis population will be the ITT population, consisting of all randomized patients.

Patients in the ITT population will be analyzed according to the treatment group allocated by randomization.

### **2.3.3 Safety population**

The safety analysis population is defined as the randomized patients who actually received at least 1 dose or part of a dose of the IMP, analyzed according to the treatment actually received.

## **2.4 STATISTICAL METHODS**

### **2.4.1 Demographics and baseline characteristics**

Parameters described above (Section 2.1.1 Demographic and baseline characteristics) will be summarized by treatment group and overall using descriptive statistics.

Unless otherwise specified, parameters will be summarized on the randomized population analyzed in the treatment group to which they were randomized. Similar analyses will be done on the safety population and will be included in the appendices if the size of the safety population is different (>10%) from the size of the randomized population for any treatment group.

P-values on demographic and baseline characteristic data will not be calculated.

### **2.4.2 Concomitant medications**

Baseline medications and devices will be presented for the randomized population and summarized by treatment group.

### **2.4.3 Extent of investigational medicinal product exposure and dose titration**

The extent of IMP exposure and compliance will be assessed and summarized by actual treatment received within the safety population.

Duration of IMP exposure in days, regardless of intermittent discontinuations, is defined as:

Last dose of double-blind IMP – first dose of double-blind IMP +1

The number (%) of patients who were up-titrated to 400 mg by Visit 7 (Month 8) will also be summarized in the sotagliflozin group.

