### 5.2 SECONDARY

- To demonstrate that, when compared to placebo, in the total patient population, sotagliflozin reduces the total number (ie, including recurrent events) of the following clinical events:
  - Cardiovascular death, HHF, or urgent HF visit (see [Appendix B](#))
- To demonstrate that, when compared to placebo, sotagliflozin reduces:
  - Cardiovascular death in patients with LVEF <50%
  - All-cause mortality in patients with LVEF <50%
  - The composite of positively adjudicated sustained  $\geq 50\%$  decrease in eGFR from Baseline (for  $\geq 30$  days), chronic dialysis, renal transplant or positively adjudicated sustained eGFR <15 mL/min/1.73 m^2 (for  $\geq 30$  days) in the total patient population
  - Cardiovascular death in the total patient population
  - All-cause mortality in the total patient population
- To demonstrate the safety and tolerability of sotagliflozin in the total patient population

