Patients will return a week later at Visit 4 (Day 15). Clinical safety and tolerability (including vital signs and collection of AEs, including EOSIs, AESIs, and SAEs) will be assessed and laboratory results from the prior week (including serum creatinine) will be reviewed, and new laboratory samples (blood and urine) will be collected. If in the opinion of the Investigator the patient's clinical condition is satisfactory and the patient has tolerated the investigational medicinal product (IMP) well without evidence of volume depletion, symptomatic hypotension (eg, dizziness, lightheadedness), or other AEs intolerable to the patient such as severe polyuria or nocturia, the dose will be up-titrated to sotagliflozin 400 mg or matching placebo qd until the next visit.

The patient will then return for Visits at Month 1 (Day 29), Month 4, and every 4 months thereafter until the end of the study.

If the patient does not meet up-titration criteria for safety reasons (eg, hypotension), the Investigator will have the option of either continuing IMP at the dose of 200 mg or placebo, with the optional adjustment of concomitant medications, or discontinuing IMP temporarily. If the dose is not up-titrated for safety reasons, the Investigator should make all attempts to up-titrate the dose at 1 of the next 3 subsequent visits: Visit 5 (Month 1), Visit 6 (Month 4), or Visit 7 (Month 8). In patients who cannot reach the dose of 400 mg or matching placebo during the first 8 months after Randomization (Visit 7), the dose of 200 mg or matching placebo will be used throughout the study. If at any time during the study, the dose of 400 mg or placebo is not well-tolerated, the dose can be down-titrated (to 200 mg or matching placebo), temporarily discontinued, or if medically necessary, permanently discontinued. All IMP discontinuation should initially be considered as temporary unless permanent discontinuation is mandated by the protocol.

If a patient permanently discontinues treatment with IMP prematurely, the patient will undergo a premature End-of-Treatment (pEOT) Visit as soon as possible. Every effort will then be made to have the patients return to the site at the times corresponding to their scheduled visits, until the Study Closeout Visit. For patients who prematurely permanently discontinue IMP, the Study

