#### 8.1.1 Dose up-titration and adjustments

##### 8.1.1.1 Dose up-titration

Patients will receive sotagliflozin 200 mg or placebo from Visit 2 and will continue this regimen qd until the next visit.

Patients will return a week later at Visit 3 (Day 8). Clinical safety and tolerability (including vital signs and collection of AEs, including EOSIs, AESIs, and SAEs) will be assessed and blood (including serum creatinine) and urine laboratory samples will be collected. Patients will continue to receive sotagliflozin 200 mg or matching placebo qd until the next visit.

Patients will return a week later at Visit 4 (Day 15). Clinical safety and tolerability (including vital signs and collection of AEs, including EOSIs, AESIs, and SAEs) will be assessed and laboratory results from the prior week (including serum creatinine) will be reviewed, and new

laboratory samples (blood and urine) will be collected. If, in the opinion of the Investigator the patient's clinical condition is satisfactory and the patient has tolerated the IMP well without evidence of volume depletion, symptomatic hypotension (eg, dizziness, lightheadedness), or other AEs intolerable to the patient such as severe polyuria or nocturia, the dose will be up-titrated to sotagliflozin 400 mg or matching placebo qd until the next visit.

If the patient does not meet up-titration criteria for safety reasons (eg, hypotension), the Investigator will have the option of either continuing IMP at the 200 mg dose or placebo, with the optional adjustment of concomitant medications, or discontinuing IMP temporarily. If the dose is not up-titrated for safety reasons, the Investigator should make all attempts to up-titrate the dose at 1 of the next 3 subsequent visits: Visit 5 (Month 1), Visit 6 (Month 4), or Visit 7 (Month 8). In patients who cannot reach the dose of 400 mg or matching placebo during the first 8 months after Randomization (Visit 7), the dose of 200 mg or matching placebo will be used throughout the study. If at any time during the study, the 400 mg dose or placebo is not well-tolerated, the dose can be down-titrated (to 200 mg or matching placebo), temporarily discontinued, or if medically necessary, permanently discontinued. All IMP discontinuation should initially be considered as temporary unless permanent discontinuation is mandated by the protocol.

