### **11.4.1 Extent of study treatment exposure and compliance**

The extent of study treatment exposure and compliance will be assessed and summarized by actual treatment received for the safety population.

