#### ***11.4.1.1 Extent of investigational medicinal product exposure***

Duration of IMP exposure is defined as: last dose date – first dose date + 1 day, regardless of unplanned intermittent discontinuations.

The number (%) of patients randomized and exposed to double-blind IMP will be presented by specific time periods for each treatment group. The time periods of interest will be defined in the SAP.

Descriptive statistics of duration of treatment exposure (number, mean, SD, minimum, median, and maximum) and cumulative exposure in patient year will also be presented by treatment group for the safety population.

The number (%) of patients with an up-titration as well as number (%) of patients with an up-titration followed by a down-titration will be summarized.

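### SAP 2.4.3 summarizes up-titration in the sotagliflozin group only and plans no down-titration output, so the planned tables do not show whether failure to reach or hold the two-tablet dose differs from placebo

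*SAP*

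**What the plan says.** SAP 2.4.3 opens with a rule that covers both arms: "The extent of IMP exposure and compliance will be assessed and summarized by actual treatment received within the safety population". It then defines duration: "Duration of IMP exposure in days, regardless of intermittent discontinuations, is defined as" last dose minus first dose plus one. Its only statement on titration is "The number (%) of patients who were up-titrated to 400 mg by Visit 7 (Month 8) will also be summarized in the sotagliflozin group". The rest of the SAP plans no titration output and does not mention down-titration.

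Protocol 11.4.1 sets the same two-arm rule, with exposure and compliance "summarized by actual treatment received for the safety population". Under it, 11.4.1.1 plans the number (%) of patients with an up-titration, and adds that the "number (%) of patients with an up-titration followed by a down-titration will be summarized". Neither is limited to one arm.

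Protocol 8.1.1.1 titrates both arms alike: if the criteria are met at Visit 4, "the dose will be up-titrated to sotagliflozin 400 mg or matching placebo qd until the next visit". Protocol 6.1.2 makes this conditional on the investigator judging that the patient has tolerated treatment "without evidence of volume depletion, symptomatic hypotension (eg, dizziness, lightheadedness), or other AEs intolerable to the patient such as severe polyuria or nocturia". Protocol 8.1.1.2 allows down-titration in either arm at any time if the higher dose is not well tolerated. Protocol 5.2 lists as a secondary objective "To demonstrate the safety and tolerability of sotagliflozin in the total patient population".

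SAP 1.1 gives the SAP precedence where it differs from the protocol.

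**The concern.** Placebo patients move from one tablet to two under the same blinded rules. The share who never reach two tablets, or who reach them and are cut back, can therefore be set against a concurrent randomized control. The protocol planned to show it by treatment received; the SAP keeps one arm and one half of the measure.

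A sotagliflozin-only percentage mixes drug intolerance with causes that also act in the placebo arm: background hypotension, progression of heart failure, death, and study closure before the titration window ended. Without the placebo figure a reader cannot separate these. At stake is part of the tolerability description, and some context for the SAP's own test of whether the hazard ratio differs before and after 240 days, which SAP 2.4.4.1 identifies as the end of the up-titration window.

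**Working it through.** The plan states no titration rate, so there is no figure to reproduce. The check is a comparison of texts, followed by a short illustration of precision.

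**1. The two documents side by side**

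| Item | Protocol 11.4.1 and 11.4.1.1 | SAP 2.4.3 |
|---|---|---|
| Up-titrated, number (%) | Yes, by treatment received | Yes, sotagliflozin only, by Visit 7 |
| Up-titrated then down-titrated, number (%) | Yes, by treatment received | Not mentioned |
| Change listed in SAP Appendix D | Not applicable | No |

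The protocol text used is amended protocol 01. The SAP refers to a later Amendment 2, which is not among the documents. The Amendment 2 items described in Appendix D do not concern titration summaries.

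**2. Whether another planned output fills the gap**

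- Exposure duration ignores interruptions and carries no dose.
- Compliance is judged in protocol 11.4.1.2 against the dose the protocol requires. A patient kept on one tablet under the titration rules can be fully compliant.
- Volume-depletion events and treatment-emergent adverse events are shown by arm (SAP 2.4.5.1). They record that an event occurred, not whether the two-tablet dose was reached or held.
- Adverse events leading to permanent discontinuation are shown by arm. Protocol 10.3 makes permanent discontinuation a last resort and asks that a reduction to one tablet be considered before a temporary stop. The response to intolerance that the protocol steers towards is thus the one with no SAP output.

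**3. Early closure**

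SAP 1.1 says enrollment closed in March 2020. SAP 2.4.4.4 gives May 1, 2020 as the date sites were told to complete end-of-study contacts. Counting 240 days back gives September 4, 2019. Patients randomized after about that date had less than the full titration window by May 1, 2020. This truncation acts in both arms, so a placebo column would show roughly how much non-attainment it accounts for.

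**4. What a two-arm table could show (assumed values)**

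The documents give neither the number enrolled nor any titration rate. For an assumed common proportion p not reaching two tablets and n per arm, the 95% CI half-width for the difference is 1.96 × √(2p(1 − p)/n). For example, p = 0.10 and n = 500 gives 1.96 × √(0.18/500) = 3.7 points.

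| n per arm | p = 10% | p = 20% | p = 30% |
|---|---|---|---|
| 500 | 3.7 | 5.0 | 5.7 |
| 1000 | 2.6 | 3.5 | 4.0 |
| 2000 (planned 4000 ÷ 2) | 1.9 | 2.5 | 2.8 |

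Half-widths are in percentage points. With 400 per arm and assumed attainment of 70% v 76%, the half-width is 1.96 × √((0.70 × 0.30 + 0.76 × 0.24)/400) = 6.1 points, so a 6-point difference would not be resolved. The one-arm row gives no between-arm difference at any n.

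**The case against.** The case against has real weight.

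- **Related harms are compared by arm.** The volume-depletion term list in SAP Appendix C includes hypotension, orthostatic hypotension, dehydration, postural dizziness, presyncope and syncope. Polyuria and nocturia would appear in the tables by preferred term. Protocol 10.4.3 has medically relevant laboratory or vital-sign abnormalities that lead to a dose change recorded as adverse events. A reader might infer that the SAP drops the between-arm tolerability comparison; it does not. This objection stands.
- **The data exist.** Protocol 10.2 lists doses of study treatment among the source data. A reader might infer that the comparison has become impossible; it is only absent from the planned outputs. This stands.
- **The SAP is silent on down-titration rather than contrary to the protocol.** Precedence applies where the documents differ, so the protocol's down-titration summary arguably survives. This stands, although no SAP output carries it out.
- **The one-arm figure has a use.** It describes the dose behind the efficacy result. A reader might call it uninterpretable; that is too strong, because it is valid as a description of exposure. This stands.
- **Titration is not a safety endpoint.** It rests on investigator judgment and is affected by death and early closure, so nothing supports ranking it as the trial's most direct measure of intolerance. Tolerability is also absent from the SAP's own secondary objectives, and Appendix D claims to list only key changes. These points limit the importance of the omission but do not explain it.

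None of these supplies the missing contrast: none of the retained tables shows, by arm, who reached two tablets and who was later reduced.

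**Conclusion.** The point holds as a minor reporting inconsistency. The SAP narrows a two-arm protocol summary of up-titration to one arm, plans no output for down-titration, and gives no reason. Its planned tables consequently do not show whether failure to reach or hold the two-tablet dose differs from placebo.

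No hypothesis, alpha allocation, power figure or primary analysis is affected. The size of any difference is unknown, and the half-widths shown depend on assumed enrollment and rates. The conclusion itself rests only on the text of amended protocol 01 and the SAP, and on both arms being titrated under the same blinded rules. The documents do not support the stronger claim that drug intolerance will go unexamined.

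**What to change.** Replace the titration sentence in SAP 2.4.3 with wording to this effect: *For the safety population, by treatment group, summarize the number (%) of patients up-titrated to two tablets (400 mg or matching placebo) by Visit 7, and the number (%) up-titrated and later down-titrated.* Optionally, show separately the patients who died or were closed out before Visit 7 without up-titration, so that truncation is not read as intolerance.

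Counts and percentages are enough; the protocol asks for no test or interval. If the one-arm summary is deliberate, list the change in Appendix D with its reason.

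The cost is one sentence, one table column and one row, from dose records kept for both arms. Nothing changes in dosing, titration rules or patient management.
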